**10.0 Study Design / Methods**

- Please see the study timeline above. Potential subjects will be phone screened and if appropriate scheduled for a consent meeting and then baseline assessments. They will then be given the video showing how to use the device. MUSC research assistants will then ship a device (and urine pregnancy test) to subjects. They will then have a training session online with MUSC RA's. Then, for each session initially they will do this online with MUSC RA's watching and rating and assisting if needed. They will complete a checklist of how well the subject administers the device. After three sessions if the subject is competent, they will self administer the device after that if they wish. All subjects can ask to have the RA online during any and all treatments if they wish. All sessions are immediately put into the database and the MUSC RA will daily monitor this and make sure the subject has correctly performed the session with no adverse events. If a subject misses a session the RA will call and talk about this. There will be immediate questions before and after each session, as well as the weekly online battery. There are also weekly online assessments and at 4,6,8 and 12 weeks after study start.

*Procedures performed to lessen the probability or magnitude of risks.*

We are excluding subjects with strokes or who are hemodynamically unstable. All sessions will be seated or even reclined if there are problems. Initial sessions are done with the MUSC RA and Soterix staff online. All session data and heart rate are sent immediately to the database and will be checked daily by research staff.

*How all drugs and devices will be used in the research (e.g. dose, dosage form, etc.)*

The device is taVNS applied to the left or right ear at two times the amplitude for perceptual threshold. This intensity of taVNS has been

used in MUSC IRB 1 monitored studies in Parkinson's Disease, Stroke Patients, Newborns and healthy volunteers. The dose for each session is *25Hz, 500us pulse width, 60s ON, 30s OFF, 1 hr. duration.*

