### 14.0 Withdrawal of Subjects

- *Describe anticipated circumstances under which subjects will be withdrawn from the research without their consent, including stopping participation for safety reasons.*

taVNS has been a very safe procedure and we do not anticipate subject withdrawal due to taVNS side effects. We will be monitoring each session and if a patient is extremely hemodynamically sensitive to the device we might consider terminating. Severely worsening of symptoms would be another reason (for example, worsening of headaches). VNS is antidepressant, antinociceptive, anti-inflammatory and anxiolytic so we do not anticipate worsening in these areas.

- *Describe any procedures for orderly termination of subjects by investigator.*

Any termination would involve online video conversations with subjects and follow the patterns used for in person documentation of the reasons and ensuring that patients have understanding and medical follow-up.

- *Describe procedures that will be followed when subjects voluntarily withdraw from the research, including partial withdrawal from procedures with continued data collection.*

As with all research, a subject can withdraw from research at any time. We will honor this and make sure the patient is safe and has good options and care and will ship the device back to MUSC.

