### Questionnaire Risk:

There are no anticipated risks to the participant. However, the participant may feel that some of the questions we ask are stressful or upsetting. If they do not wish to answer a question, they may skip it and go to the next question, or they may stop immediately. Also, being assessed for study entry, including the possibility that they may not meet criteria for entering the study may be distressing. If they become upset or distressed as a result of their participation in the research project, the research team will be able to arrange for a one on one meeting with our team psychiatrist.

Our commitment to patients is to take all reasonable steps to help them find treatments for worsening psychiatric symptoms. If the subject's psychiatric conditions worsen (specifically suicidality or suicide ideation), we will provide the National Suicide Prevention Hotline call or text number ([name]) to the subject or advise the subject to go to the nearest Emergency Department or call 911.

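### The stated response to suicidality does not require telling the team psychiatrist, and no section commits anyone to read online ratings as they arrive once sessions end at week 4

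*Combined protocol and SAP*

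**What the plan says.** **Daily check.** Section 10.0 states it twice. Under the risk-reduction procedures: "All session data and heart rate are sent immediately to the database and will be checked daily by research staff". In the account of study conduct, after saying that sessions go straight into the database: "the MUSC RA will daily monitor this and make sure the subject has correctly performed the session with no adverse events". The same section sets the ratings: "There are also weekly online assessments and at 4,6,8 and 12 weeks after study start". It also says that ratings are done online and stored in Redcap.

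**Response to worsening.** Section 15.0, Questionnaire Risk, covers three things. For a participant upset by taking part, "the research team will be able to arrange for a one on one meeting with our team psychiatrist". As a general promise, "Our commitment to patients is to take all reasonable steps to help them find treatments for worsening psychiatric symptoms". For the most serious case, "If the subject's psychiatric conditions worsen (specifically suicidality or suicide ideation), we will provide the National Suicide Prevention Hotline call or text number", or else the subject is told to go to an emergency department or call 911.

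**Withdrawal.** Section 14.0 lists worsening as grounds for stopping: "Severely worsening of symptoms would be another reason (for example, worsening of headaches"). The monitoring it mentions is of each session. On mood it says: "VNS is antidepressant, antinociceptive, anti-inflammatory and anxiolytic so we do not anticipate worsening in these areas".

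**The concern.** New-onset depression and anxiety are qualifying symptoms in section 5.0, and the exclusion list there does not mention suicidality. Participants are at home throughout, so the team learns of a crisis only through a session, a rating or a call.

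Two steps matter for safety: noticing the problem and acting on it. The action written for suicidality ends with advice to the participant. The notice step is written around stimulation sessions, and these stop at week 4 while ratings continue. The other contact triggers are also tied to treatment: section 10.0 has the research assistant call after a missed session, and the on-demand support in section 8.0 is for using the device.

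The argument in section 14.0 that mood should not worsen rests on the effects of VNS. It offers no reason for the weeks after stimulation ends. At stake is whether a participant who discloses suicidal thoughts is promptly seen by a clinician who knows the study, and whether marked worsening during follow-up is noticed when it is entered.

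**Working it through.** The plan gives no figure to reproduce on this point. The check compares the sections and does schedule arithmetic.

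**1. Routes from worsening to a clinician**

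| Route | Section | What starts it | Who is reached |
|---|---|---|---|
| Hotline number, or emergency department/911 advice | 15.0 | Psychiatric worsening, suicidality named | The participant; no team clinician named |
| Psychiatrist meeting | 15.0 | Distress resulting from participation | Team psychiatrist, if arranged |
| Adverse event reporting | 13.0 | Event recognised as an unanticipated problem or adverse event | The responsible lead or designee, who reports to the IRB |
| Serious adverse event notice | 13.0 | Event classed as serious | Safety monitoring committee |
| Termination by the investigator | 14.0 | Decision to withdraw the subject | Video conversation and medical follow-up |

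The first row is the one written for suicidality, and it names no team clinician. Rows three to five do reach the team or its committee, but each needs a prior classification or decision. None sets a prompt psychiatric contact.

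**2. What the daily check can act on**

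- Sessions (10.0): 2 per day x 6 days x 4 weeks = 48, which agrees with 24 + 24 in that section. All fall in weeks 1-4, and section 18.0 has the device returned then.
- Weeks with ratings still due but no sessions: 12 - 4 = 8.

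**3. Ratings after the last session, per patient**

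- Section 10.0, weeks 6, 8 and 12 from study start: 3.
- Section 1.0, Aim 1, at 2, 4, 6 and 8 weeks after treatment, i.e. weeks 6, 8, 10 and 12: 4.
- Section 4.0, at 2, 3, 4, 5, 6, 8 and 12 weeks, read literally as after treatment: 7, the last at 4 + 12 = week 16.

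Under every stated schedule, ratings outlast sessions.

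**4. Who reads them**

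Sections 8.0 and 10.0 have subjects complete assessments online, with data going to Redcap. Neither names a reader, a time limit or an escalation. Section 7.0 has staff communicate through the rating platform, section 8.0 has the team administer the battery serially, and section 13.0 has a team member attend each patient and record adverse events as they occur. These fit live contact at ratings, but none commits to it. The weekly battery in weeks 1-4 is not named in the daily check either, although participants are then covered by the session check.

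**5. Volume to read, if all 30 enrolled complete every rating**

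- After week 4: 30 x 3 = 90, 30 x 4 = 120, or 30 x 7 = 210.

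**The case against.** The strongest reply is that the safety net is wider than one sentence. Suicidality judged to be an adverse event must reach the person responsible for IRB reporting, and if serious it goes to the safety committee at once. Withdrawal for severe worsening brings a live conversation and medical follow-up. The psychiatrist, the promise of reasonable steps and the emergency advice all sit under one heading, and nothing says that the emergency advice replaces the psychiatrist. This stands. A reader might infer that no clinician would ever be told, or that a suicidal participant is denied the psychiatrist; the documents support neither. What remains is that the specific step for suicidality does not itself require psychiatric notification or contact.

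On detection, the reply is that the point rests on silence. Staff may be live at each rating, and the questionnaires were uploaded separately and cannot be seen here; they may contain a suicidality item or alert instructions, or neither. This also stands, so it cannot be said that follow-up ratings go unread. Live contact would close the detection gap and leave the response gap.

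A reader might also infer that worsening seen only in ratings would be lost to the analysis. That is not supported: section 4.0 lists symptom change alongside adverse events in the primary outcome, and the committee reviews accumulated data. Only the adverse event label is uncertain. Nor are sham patients in weeks 1-2 outside the net, since they have daily sessions and the stated check applies to them.

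**Conclusion.** The point holds in two limited parts. First, the written response to suicidality stops at a hotline number or emergency advice, with no required prompt notification of, or contact by, the team psychiatrist. This does not depend on how ratings are collected. Second, both statements of the daily check concern sessions, and for at least 8 weeks after these end no section commits anyone to read ratings on entry. This part is conditional, because unstated practice or the unseen questionnaires may already cover it.

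The clinical size cannot be given: the documents contain no rate of suicidality or severe worsening, and none is assumed. The case for change rests on the remote setting, the enrolment of new-onset depression without a suicidality exclusion, and the low cost of the remedy. It does not rest on a predicted number of events.

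**What to change.** **Section 15.0.** Keep the hotline, emergency department and 911 advice. Add that any reported suicidality or marked psychiatric worsening, however it comes to light, is passed promptly to the existing team psychiatrist, who contacts the participant. After that clinical review, record an adverse event where warranted and notify the safety committee if it is serious.

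**Section 10.0.** Extend the existing staff check to each questionnaire entered, through the last follow-up rating. Escalate to the psychiatrist any positive answer on a suicidality item that the uploaded scales contain, and any marked mood worsening from baseline beyond a threshold the psychiatrist sets. If the scales have no suicidality item, the mood threshold alone applies here, and the 15.0 change covers suicidality reported in other ways. An automatic Redcap alert is optional. If staff are already live at every rating, saying so would meet most of this.

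**Cost.** A short addition to each section, no new instrument, and modest review time for existing staff: 90 to 210 follow-up ratings across the trial, depending on the schedule, plus the baseline and treatment-week batteries. Some escalations will be false. Their number cannot be estimated from the documents, and recording adverse events only after clinical review keeps them out of the safety counts.

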## **12.0 Data Management**

All data will be stored in the Redcap database. The blind will be kept by the MUSC RA, but they will be blinded as well. Soterix will set the active or sham control from the company after being instructed by the MUSC RA about the randomization code number for that patient, but MUSC will have the unblind in terms of emergency.

Information about the participant (including their identifiable private information and/or any identifiable biospecimens) may have all of their identifiers removed and used for future research studies or distributed to other researchers for future research without additional informed consent from them or their legally authorized representative.

In rare cases, the device manufacturer, Soterix, may need access to minimal PHI (such as name, phone number and address) in the event there is a device malfunction. Well-trained MUSC staff will make every attempt to resolve any issues before putting Soterix in direct contact with the participant.

At a high-level analysis, we will compare the group changes in neuropsychiatric questionnaires in active versus sham taVNS using repeated measures ANOVA from baseline to immediately after last treatment and then as well over the 3-month follow-up.

Power analysis on primary outcome: As there is no real data yet on taVNS effects on NeuroCOVID patients, it is difficult to perform a formal power analysis. The repeated measures design in 15 active and 15 sham patients will allow us to detect differences with a large or moderate effect size to be used for calculating power and sample size for subsequent trials.

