##### Primary Outcome:

As this is a pilot and exploratory study, the outcomes are largely descriptive. In terms of feasibility we will assess dropout rates and compliance and subjective ratings of the device and the online only study. In terms of safety we will assess changes in blood pressure and any syncope or other adverse events. We will also examine changes in neuropsychiatric symptoms for patients presenting with different NeuroCovid symptoms.

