**8.0 Recruitment Methods**

[figure not shown]
We will screen for formerly COVID positive people in our electronic medical record (Epic) who have given permission to be contacted for research. Through our electronic medical record, we will contact MUSC COVID positive patients at least 14 days after their last test, and ask if they have residual symptoms. Subjects will sign consents and complete assessments online. We will then serially administer a broad ranging and comprehensive online battery assessing neuropsychiatric functioning and symptoms. MUSC will ship the device to subjects and they will be educated on the device use. We will provide telemedicine-based device-use support on demand if they have questions.

Please see the attached flyer.

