Subjects will receive two treatment sessions/day, 6 days per week, for two weeks (randomized), for 24 treatments in the double-blind phase. All subjects will then receive an additional two weeks – 24 more treatments. For those initially randomized to active VNS, they will thus receive up to 48 hours of VNS therapy. For those initially randomized to sham, they will still receive 24 sessions, or 24 hours of treatment. While this may seem like a lot, remember that cervical VNS is implanted and then stimulates on and off for many years. Thus, this dose is minimal compared to the large and safe database of VNS for epilepsy or depression.

*The source records, including medical or educational records that will be used to collect data about subjects.*

We will collect demographic and clinical data from the Epic Database. We will perform phone screens and then online consent and ratings. All ratings will be done online with data going into Redcap with secure access. All data collected from the device will also go to the secure online MUSC Redcap database.

*Describe data collection procedures (e.g. chart review, subject interview, etc.). Provide a description of all assessment instruments to be used. (Upload in eIRB all surveys, scripts, etc.) Include what data will be collected.*

See above. We have uploaded all database questionnaires.

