### **16.0 Potential Benefits to Subjects or Others**

A strength of this proposal is that it will allow us to pivot in the directions of greatest need in one year with a multitude of potential therapeutic targets and benefits, once initial feasibility and efficacy of the taVNS home therapy protocol has been established. The research team is experienced and are leaders in neuromodulation research and are thus uniquely capable of successfully shepherding this pilot work into a funded clinical trial. Invasive cervical VNS is FDA approved for epilepsy and depression. Noninvasive cervical VNS is FDA approved for cluster headaches. We have seen anxiolytic and antidepressant effects of taVNS. There is legitimate prospect of benefit for NeuroCovid symptoms although this is still experimental. All subjects will get the active open treatment for weeks 2-4.

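### The effect that will size the next trial has no pre-stated score or selection rule, and its comparison windows run past the sham-controlled phase

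*Combined protocol and SAP*

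**What the plan says.** The analysis is given in one sentence of section 12.0: "we will compare the group changes in neuropsychiatric questionnaires in active versus sham taVNS using repeated measures ANOVA". The periods that this sentence covers are stated as "from baseline to immediately after last treatment and then as well over the 3-month follow-up". The power paragraph that follows says that 15 active and 15 sham patients will show effects of large or moderate size, "to be used for calculating power and sample size for subsequent trials". It gives no significance level, power, standard deviation or numerical effect.

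Section 4.0 does not identify the efficacy variable. Under Primary Outcome it says "As this is a pilot and exploratory study, the outcomes are largely descriptive", lists feasibility and safety, and adds "We will also examine changes in neuropsychiatric symptoms for patients presenting with different NeuroCovid symptoms". The Secondary Outcome entry only points back to that text. Section 8.0 describes "a broad ranging and comprehensive online battery assessing neuropsychiatric functioning and symptoms", and section 10.0 says of the instruments "We have uploaded all database questionnaires". Those forms are not part of this document.

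On timing, Aims 1 and 2 and section 10.0 agree: two randomised weeks of active or sham stimulation, then two weeks in which everyone receives active stimulation. Aim 2 gives the comparison of two with four weeks as one purpose of the second phase. It also says that the next trial will address specific symptoms, without saying which.

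**The concern.** There are two separate difficulties with the number that the next trial will inherit.

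**Selection.** Several scales are compared, the target symptom is still to be chosen, and the effect size from the same data goes into the next sample-size calculation. If the choice is influenced by which scale looked best, the estimate carried forward is biased upwards. The next trial would then be too small, or aimed at a symptom picked by chance. Calling the study exploratory does not remove that bias, because it arises from how the estimate is used.

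**Timing.** Only the first two weeks are sham-controlled. A comparison made after the last treatment, or during follow-up, sets more active stimulation against less. If benefit levels off within two weeks of active use, the arms would look alike at week 4 even if the treatment works. Selection tends to push the estimate up and the crossover may pull it towards zero. There is no reason to expect the two to cancel.

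**Working it through.** **Inputs from the documents**
- Patients: 15 per arm (12.0); 30 recruited for 24 completers (6.0). The implied loss is 1 − 24/30 = 20%, and 24/(1 − 0.20) = 30 reproduces the recruitment figure. If loss is equal between arms (assumption), 12 per arm complete.
- Symptoms named in Aim 1 and section 5.0: anxiety, depression, vertigo, anosmia, headaches, fatigue, irritability, cognitive processing, so k = 8. This is an open list of eligibility examples. One score per symptom is an assumption.
- The plan states no numerical effect, so there is no effect-size figure to reproduce.

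**Other assumptions:** SD = 1, two-sided 0.05, no adjustment, common correlation ρ between scores of 0 to 0.7, and selection of the result most favourable to active.

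**Step 1. Standard error of one standardised difference,** √(2/n)
- n = 15: √(2/15) = 0.365
- n = 12: √(2/12) = 0.408

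**Step 2. Expected best of k when no effect exists,** E[max of k standard normals] × √(1 − ρ) × √(2/n). For k = 8 the first factor is 1.4236.

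| ρ | 15 per arm | 12 per arm |
|---|---|---|
| 0 | 1.4236 × 0.365 = 0.52 | 1.4236 × 0.408 = 0.58 |
| 0.3 | 0.43 | 0.49 |
| 0.5 | 0.37 | 0.41 |
| 0.7 | 0.28 | 0.32 |

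A simulation of 40,000 replicates, using the observed standardised difference, gave slightly higher values: 0.54 and 0.61 at ρ = 0, and 0.30 and 0.34 at ρ = 0.7. The result also depends on k. With independent scores at 15 per arm it is 0.31 for k = 3, 0.42 for k = 5 and 0.56 for k = 10. For one score named in advance it is 0.

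**Step 3. Chance of at least one two-sided p<0.05 favouring active**
- Independent scores: 1 − 0.975^8 = 18%.
- Simulated at ρ = 0.5: 12.7%. At ρ = 0.7: 9.5% (15 per arm) and 9.7% (12 per arm).
- One named score: 2.5%.

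**Step 4. Consequence for the next trial.** At 80% power and two-sided 0.05, n per arm = 2 × (1.96 + 0.84)²/d². A chance value of d = 0.52 gives 59 per arm and d = 0.37 gives 115, in both cases for an effect that does not exist.

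**Step 5. What each comparison time contrasts** (active sessions received at full compliance, from 3.0 and 10.0)

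| Time | Initially active | Initially sham | Contrast |
|---|---|---|---|
| End of week 2 | 24 | 0 | active vs sham |
| End of week 4, last treatment | 48 | 24 | 4 vs 2 weeks of active |
| Follow-up | 48 | 24 | 4 vs 2 weeks of active, after stopping |

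Of these times, only the first answers the question in the wording of section 12.0.

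**The case against.** The strongest reply is that this is a declared pilot, with largely descriptive outcomes and with feasibility and safety listed first. Strict familywise control is not expected of such a study. That stands: the absence of a multiplicity adjustment is not in itself a fault here.

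Several stronger readings are also unsupported.
- A reader might infer that the symptom with the best result will be taken forward. No section says so. The only language on direction, in Aim 2 and section 16.0, speaks of need and not of observed effect. Best-of-eight selection is a scenario that the plan leaves open.
- A reader might infer a significance test on every questionnaire. Section 12.0 uses an unqualified plural, and presents it as a high-level outline without a decision rule.
- A reader might quote 1 − 0.95^8 = 34% as the risk of a false efficacy finding. That figure also counts results favouring sham. For results favouring active it is 18% at most under these assumptions.
- A reader might take "once initial feasibility and efficacy of the taVNS home therapy protocol has been established" as a success criterion. It is in the benefits section, is qualified as initial, and sets no threshold.

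The number of scores is also unknown, and some of the symptoms, such as anxiety, depression and irritability, are unlikely to be independent, so 0.52 SD lies towards the upper end. Finally, patients enter with different symptoms, so a single symptom scale could be irrelevant to many of the 30. That limits what the fix can demand.

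None of this supplies the missing score, rule or sham-controlled time. The uploaded questionnaires may list the instruments, but a list does not say which one supplies the sizing estimate.

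**Conclusion.** The concern holds in a limited form. Sections 4.0 and 12.0 fix neither the score behind the effect size meant for the next trial nor how it will be chosen. On its natural reading, the last-treatment comparison takes place when both arms have had two weeks of active stimulation. Section 12.0 does not define the last treatment, and a reading that stops at the blinded phase is possible, but the four-week schedule makes week 4 the plainer one.

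The size of the selection problem is conditional. If the most favourable of about eight scores were carried forward, the expected effect with no true benefit would be about 0.3 to 0.6 SD, and the chance of a nominally significant result favouring active about 9.5% to 18%. Fewer or more highly correlated scores lower both figures. The timing problem needs none of these assumptions, since it follows from the schedule. This should be corrected; it does not undermine the feasibility and safety aims.

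**What to change.** Revise section 12.0 before unblinding.

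1. Make the end of week 2, the last sham-controlled assessment, the time for the active-versus-sham estimate that will size the next trial. The weekly ratings in Aim 1 and section 10.0 already cover it.
2. Pre-state the score that supplies the estimate: a global score if the existing battery has one, or each patient's main presenting symptom, identified from baseline data, on a standardised scale. Alternatively, state a selection rule that does not depend on the observed results.
3. Report all scales as estimates with 95% CIs, labelled exploratory. Holm adjustment of any p-values shown is optional.
4. Analyse week 4 and follow-up as four versus two weeks of active stimulation, in line with Aim 2.
5. In Aim 2 and section 16.0, describe the result as an effect estimated, not as efficacy established.

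The cost is about a paragraph in section 12.0 and a change of wording elsewhere. Recruitment, treatment and data collection are unaffected. The headline effect will probably look less favourable, and a single score may be less relevant to some patients.
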